5 PROJECT

6 PATIENTS AND METHODS

7 All patients with non-traumatic SCI consecutively admitted to three Italian SCI centers (IRCCS  
8 Fondazione Santa Lucia, Montecatone Rehabilitation Hospital and Istituti Clinici Scientifici  
9 Maugeri IRCCS of Pavia) between January 1st 2017 and June 30th 2020 have been prospectively  
10 enrolled in the study.

11 The study has been registered at [Clinicatrials.gov](https://www.clinicaltrials.gov).

12 The study was approved by the ethic committee of IRCCS Fondazione Santa Lucia and all the  
13 patients signed an informed consent to the study.

14 Inclusion criteria were: having a non-traumatic SCI in the acute / subacute phase with any level and  
15 severity (ASIA Impairment Scale) of injury and having a cognitive status that allows collaboration  
16 in the exam.

17 Exclusion criteria were the presence of dementia or cognitive decline; having a pathology of the  
18 peripheral nervous system that may affect the evaluation of ISNCSCI; having a multiple sclerosis.

19 The following data were prospectively recorded:

20 - Recording of demographic and clinical history data. Concerning the onset of lesion, for the  
21 ischemic and inflammatory groups reference was made to the appearance of the first symptoms,

22 while for the neoplastic and spondylogenetic myelopathies we referred to the date of surgical  
23 intervention which is usually accompanied by a worsening of the clinical picture.

24 - Evaluation of neurological conditions according to the International Standards For Neurological  
25 Classification of Spinal Cord Injury (ISNCSCI) (Revision 2015) (23) with registration of right and  
26 left motor and sensory level and of the Neurological Level of Injury (NLI), of the total motor score  
27 (MS), of upper extremities (UEMS) and lower extremities (LEMS) motor scores, light touch and  
28 pin prick sensory scores, and ASIA Impairment Scale (AIS). This assessment was carried out by  
29 two different experienced examiners (Table 1) in each center, 48-72 hours apart. One of the two  
30 examiners also assessed the functional status of the patients through the Spinal Cord Independence  
31 Measure (SCIM) version 2 or 3 (24).

32 - The patients were evaluated at admission with the possibility of repeating the evaluation also  
33 during rehabilitation stay and at discharge,.

34 Statistics

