35 Descriptive statistics: mean and standard deviation (SD) for quantitative data; frequencies and  
36 percentages for qualitative ones. Normality of data was assessed by Shapiro-Wilk test. The NLI and  
37 the AIS grade have been transformed into numbers and treated as ordinal variables. For the NLI the  
38 level C1 corresponds to 1, and the level S4-5 to the number 29. For the AIS grade A correspond to 1  
39 and grade E to 5.

40 Validity and reliability represents the main measurement psychometric properties of instruments.  
41 The validity of instrument means that it measures what it is intended to measure. (25) while  
42 reliability refers to its stability over time (26).

43 Different aspects of reliability were assessed with appropriate tests: correlation (Spearman), test-  
44 retest reliability (Krippendorff's Alpha) and internal consistency (Cronbach's Alpha) (27, 28). For  
45 motor and sensory scores, we also compared the data of the two examiners by means of Wilcoxon  
46 matched pair test to evaluate if there was any significant difference.

47 As to the levels of injury (Neurological Level of Injury, left and right sensory and motor level of  
48 injury) and AIS grade the agreement between the two examiners regarding was assessed through the  
49 Krippendorff's Alpha. Furthermore, for the assessment of the levels, we compared the levels  
50 established by the two examiners, by counting the difference (1 level, 2 or more levels) in cases  
51 where assessments differed.

52 We evaluate psychometric properties of AIS scale on all sample and in each pathology subgroups.

53 As currently there is no gold standard for the neurological evaluation of persons with SCI other than  
54 the ISNCSCI, we have evaluated the convergent construct validity of the Standards through a  
55 Spearman correlation between the total motor scores, the upper and lower extremities motor scores  
56 and the total SCIM score as well as the subscores "Self-care" and "Mobility". This correlation was  
57 performed by means of Spearman test.

58 According to Landis and Koch (29), we interpreted ICC values and the level of agreement by  
59 Kappa-values as follows:  
60 0–0.1-virtually none  
61 0.1–0.4-slight  
62 0.41–0.6-fair  
63 0.61–0.8-moderate  
64 0.81–1-substantial  
65 All analyses were performed with SPSS 22.  
66 Significance was set at  $p < 0.05$   
67 Data have been reported according to the Guidelines For Reporting Reliability And Agreement  

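### The Wilcoxon examiner comparison of motor and sensory scores has only a p-value as readout, so it shows neither agreement nor the size of any shift; report the mean difference with CI and limits of agreement.

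*Combined protocol and SAP*

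**What the plan says.** The Statistics part of PATIENTS AND METHODS first names the reliability tools: "Different aspects of reliability were assessed with appropriate tests: correlation (Spearman), test"-"retest reliability (Krippendorff's Alpha) and internal consistency (Cronbach's Alpha"). It then adds that, for "motor and sensory scores, we also compared the data of the two examiners by means of Wilcoxon" "matched pair test to evaluate if there was any significant difference". The threshold comes at the end of the section: "Significance was set at" p < 0.05. Sidedness is not stated.

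Agreement is graded on verbal bands: "According to Landis and Koch (29), we interpreted ICC values and the level of agreement by" kappa. These bands do not refer to the Wilcoxon p.

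For injury levels and AIS grade, the section names Krippendorff's Alpha explicitly as the measure of examiner agreement. For levels it also counts how often the examiners differ by one level or by two or more. Motor and sensory scores get no comparable summary of size. The paired data come from "two different experienced examiners (Table 1) in each center, 48-72 hours apart. One of the two" examiners also scored SCIM. The plan states no number of patients, expected SD of differences, tie rate or acceptable difference in points.

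**The concern.** In a two-examiner study the useful statement about the scores is how far apart the examiners are, in points, and how certain that is. A signed-rank test of zero shift answers a narrower question, and its p-value can mislead in three ways:

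- Non-significance may mean only that there were few pairs, or few untied pairs, since zero differences are dropped.
- Significance may reflect a shift too small to matter.
- Large errors that go equally in both directions leave the test silent, although agreement is poor.

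If the published text rests on a statement that no significant difference was found, readers may take it as support for reliability, and nothing else planned for these scores gives a size in points to correct them. Spearman correlation is unaffected by a constant shift, and an agreement coefficient has no units.

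**Working it through.** The plan has no figure to reproduce. Every N, SD, shift and tie rate below is an assumption chosen to show a range. The 0.05 level is from the Statistics section, taken as two-sided.

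**1. A real shift that is not significant.** Differences were simulated as rounded normal values with mean 2 points and SD 6 or 10, zeros dropped, 2,000 runs per cell. Proportion with p ≥ 0.05, from SD 6 to SD 10:

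| Pairs | Not significant |
|---|---|
| 40 | 49–78% |
| 80 | 17–58% |
| 130 | 4–39% |

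Hand check for N = 80, SD 10: z = 2/(10/√80) = 1.79, and power ≈ Φ(1.79 − 1.96) = 0.43, so about 57% are missed. If such a study observed exactly a 2-point mean difference, the 95% CI would be 2 ± 1.96 × 10/√80 = 2 ± 2.19, or −0.19 to 4.19. The p-value would say there is no significant difference, while the interval still allows about 4 points.

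**2. Few untied pairs.** With m untied pairs, the smallest exact two-sided p is 2 × (1/2)^m: 0.0625 for m = 5 and 0.031 for m = 6. An exact test therefore cannot reject with 5 or fewer. With the uncorrected normal approximation the limit is one pair lower. For m = 5, z = 7.5/√13.75 = 2.02 (p about 0.043). For m = 4, z = 5/√7.5 = 1.83 (p about 0.07). The plan does not say which version is used. In simulation (normal approximation) with 90% ties and a 5-point shift (SD 3) in the remaining pairs, rejection was 3% at N = 20, 46% at N = 50 and 94% at N = 100. The problem fades as N grows.

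**3. A small shift that is significant.** For a 0.5-point shift, SD 2, N = 130: z = 0.5/(2/√130) = 2.85, and power ≈ Φ(2.85 − 1.96) = 0.81. Simulation gave 78–79%. The corresponding interval is 0.5 ± 1.96 × 2/√130 = 0.5 ± 0.34, or 0.16 to 0.84, which shows how small the shift is. Separately, on an assumed 0–100 score (mean 60, SD 22), a 1-point shift with SD of differences 2 was significant in 50% of runs at N = 20, 90% at N = 50 and 99.5% at N = 100, with ICC and Krippendorff's Alpha at about 0.994.

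**4. Large symmetric disagreement.** On the same assumed score, with no shift built in and error SD 15 or 20 points, rejection was about 4–8% for N from 20 to 200, close to the nominal 5%. ICC and alpha fell to about 0.80 and 0.70. Before truncation to the scale, the limits of agreement would be ±1.96 × 15 = ±29.4 and ±1.96 × 20 = ±39.2 points. More patients do not cure this, because the test is not aimed at spread.

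**5. Does a Hodges-Lehmann interval solve it?** Not where ties are common. With 70% zero differences, about 0.7 × 0.7 = 49% of the pairwise averages are exactly zero and the rest split between positive and negative, so their median is usually zero. In simulation with zeros kept, the 95% interval collapsed to [0, 0] in 55–58% of runs at N = 40, 87–93% at N = 80 and 98–99% at N = 130. The mean difference does not have this defect.

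**The case against.** A reader might infer that the plan treats a non-significant Wilcoxon p as proof of reliability. The documents do not support that. No such rule is stated, the word 'also' makes the test a supplement to Spearman and the two alphas, and the grading bands concern ICC and kappa. In the 1-point example above, ICC and alpha stay near 0.994, so a reader with those coefficients would not be badly misled. This stands, and it keeps the point modest.

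It does not remove the point. Krippendorff's Alpha is tied explicitly to levels and AIS grade. For motor and sensory scores it is covered only by the general sentence, and ICC appears only in the grading bands. Wilcoxon is the one examiner comparison named specifically for the scores.

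A second objection is that heavy ties are speculative. This also stands. Ties are plausible for upper-extremity scores at the maximum in low lesions, but the documents give no rate, and nothing suggests it for the other scores. Moreover, a 2-point shift confined to 30% of pairs is a mean shift of only 0.3 × 2 = 0.6 points. Failing to flag it is not clearly a failure, so the verdict does not rest on high-tie scenarios.

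Third, an interval for the mean shift is as blind to symmetric disagreement as the Wilcoxon test. That is correct, and it is why limits of agreement belong in the fix.

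**Conclusion.** The point holds in a limited form. For motor and sensory scores, the Wilcoxon p addresses only systematic shift and should not be read as evidence for or against agreement. The plan does not say it will be, but it provides no estimate in points that would prevent it. That logic needs no assumed number. Its size does: under the assumed inputs, a 2-point shift goes unflagged in anything from 4% to 78% of studies depending on N and SD, a 0.5-point shift can be flagged about 80% of the time, and disagreement with limits near ±30 to ±40 points is flagged hardly more often than chance. Since agreement coefficients are also planned, this is an inexpensive improvement in analysis and reporting, not a flaw that invalidates the study.

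**What to change.** For total motor score, UEMS, LEMS, light touch and pin prick, report:

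- the mean paired examiner difference with a 95% CI (bootstrap if the differences are skewed);
- the 95% limits of agreement;
- the number of pairs with zero difference.

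Base the conclusion on systematic examiner difference on these figures, beside the agreement coefficient, and keep the Wilcoxon p as a descriptive line. Do not use the Hodges-Lehmann interval where many pairs tie. A margin in points is optional. If one is used, the investigators should fix it before seeing the results. The plan is written largely in the past tense, so if results are already known the margin should be labelled post hoc.

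The cost is a few more figures per score from data already collected. Some scores may read as inconclusive where they would otherwise have read as showing no significant difference.
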